1 BACKGROUND INFORMATION

1.1 Significance

Our objective is to study effects of a contraceptive vaginal ring (CVR) containing estrogen and progesterone (NuvaRing) on vaginal bacteria (the vaginal microbiome), local immunity, and lower genital tract infection in women. Emerging data suggest a favorable effect of this CVR on vaginal bacteria, specifically hydrogen peroxide-producing lactobacilli (LB), which are supported when the vagina is under the influence of estrogen.^{1,2} These lactobacilli are critical for defense against infection with HIV and other sexually transmitted infections (STI). Bacterial vaginosis (BV) is characterized by loss of these LB and instead, overgrowth of a mix of anaerobic bacteria. BV significantly increases risk of STI/HIV, including genital herpes caused by HSV2.^{3,4} BV is characterized by declines in protective immunologic mediators (certain defensins, secretory leukocyte protease inhibitor (SLPI)) and increases in inflammatory cytokines and chemokines,⁵ alteration of cervical immune cell populations⁶ and activation of local immune cells, including T cells.⁷ Whether local delivery of hormones through a product like the CVR restores the lactobacilli and the protection they provide from BV and STI/HIV is unknown. In contrast, the contraceptive systemic depot progesterone—commonly used worldwide—may independently increase risk of HIV acquisition and transmission.⁸ Our overarching hypothesis is that NuvaRing contributes to reduction in BV, healthy markers of cervicovaginal immune response and decreased rates of HSV2 shedding. Long-acting vaginal delivery of hormonal contraception as the foundation of “multicomponent prevention” – for example, delivery systems that can combine activity against unintended pregnancy, HIV, and other STI—has become a major focus for scientists, advocates, and funders alike,⁹⁻¹¹ but effects on the vaginal environment need careful definition before broad implementation.

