infections, and acquisition of multiple STI, including HSV2 and HIV.¹⁴ BV may elevate these risks in several ways, including activation of local immune cells. Finally, recent data indicate that onset of menstruation triggers key shifts in local vaginal bacteria, and in many women, may actually precipitate BV. Continuous use of the NuvaRing (use for four weeks, then replace) suppresses menstruation, and is increasingly used by many women with excellent reports of acceptability and safety. Whether this suppression of menstruation could suppress BV recurrence is not known.

Although short-term antibiotic therapy improves symptoms and restores *Lactobacillus* predominance in most women with BV, up to 20% of women fail routine therapy. In addition, BV recurrence after successful therapy is the rule. Recurrence is likely caused by failure to recolonize the vagina with desirable lactobacilli, which requires adequate vaginal estrogenization. In one study, women who used the NuvaRing for 3 consecutive 28-day cycles had higher quantities of desirable vaginal lactobacilli relative to women who used oral contraceptive pills containing 20 µg ethinyl estradiol and 100 µg levonorgestrel.¹ The NuvaRing releases 120 mcg/day of ENG (the active metabolite of desogestrel, a progesterone) and 15 mcg/day of ethinyl estradiol (the estrogen component). While generally well tolerated, incidence of local complaints (increased vaginal discharge or discomfort) with continuous CVR use is higher than those reported by OC users;¹⁵ thus, the risk: benefit ratio of this approach needs careful assessment.

Pregnancy is also an independent risk for HIV acquisition and transmission, when acquisition confers high rates of perinatal transmission.^{16,17} However, systemic depot progesterone, commonly used worldwide, may independently increase risk of HIV acquisition and transmission.⁸ Increased HIV risk related to hormonal contraceptive use would be of global public health importance, given the large number of women using such methods. In a recent technical report, the World Health Organization noted that “expansion of contraceptive method mix and further research on the relationship between hormonal contraception and HIV infection is essential.”¹⁸

For all of these reasons, then, a careful study of the microbiological, clinical, and immunologic benefits of the CVR is a high scientific and public health priority.

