9 STATISTICAL CONSIDERATIONS

9.1 Outcomes

Aim 1. The primary outcome will be quantity of *L. crispatus* measured by qPCR at all available follow-up visits and will be compared during five months of CVR use to one month prior to CVR use. Secondary outcomes will be BV defined clinically by Amsel and confirmed by Nugent criteria at any follow-up visit, quantities of other BVAB defined by qPCR assay, and reported genital adverse events. Quantity and presence of other lactobacilli and BVAB species detected by PCR will be assessed using the methods outlined above. All available follow-up observations will be used. Quantity of *L. crispatus* will be log transformed and analyzed using a linear mixed model with subject random effect to account for correlation within person. Binary outcomes will be analyzed using generalized estimating equations with log link and robust standard errors to estimate relative risks while accounting for correlation.

Aim 2. The outcomes of interest will be compared within participants, using each woman as her own control; observations from the time prior to CVR initiation will be compared to those collected during CVR use. We will use methods for Normal data and then use non-parametric approaches or dichotomize and use binomial link GEE if data are highly skewed and cannot be transformed into a Normal distribution. Some analyses will be exploratory; we will compare quantities of several immune mediators noted above by CVR use. These comparisons will not likely be independent, so we will adjust for multiple comparisons by permutation procedure. We will also correlate concentrations of immune mediators with qPCR results in Aim 1 to test the hypothesis that higher concentrations of protective lactobacilli will be associated with higher levels of protective mediators, and lower levels of inflammatory cytokines/chemokines. Continuous variables between comparison groups will be compared using t-tests or Wilcoxon rank-sum tests, and dichotomous variables will be compared by chi-square tests or Fisher's exact tests. Linear mixed effects models or generalized estimating equation (GEE) models will be used to examine whether outcomes (mediator concentrations, vaginal bacterial

quantities) differ significantly between comparison groups after adjustment for confounding factors identified through univariate analysis. All analyses will assume a two-sided significance level of 0.05.

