Aim 3. The primary outcomes will be (1) incidence of BV at all available follow-up visits, and (2) time to BV during four months of CVR use relative to the two months prior to CVR use. For secondary analysis, we will measure the quantity of HSV-2 by PCR. This will be log transformed and association with CVR use examined using a linear mixed model as for Aim 1. *Sample size calculation:* Data from our prospective studies of BV were used to estimate the likelihood of these conditions occurring during follow-up. Over six months of observation, we have documented BV recurrence rates after cure of an initial BV episode of 28 / 100 person-years in absence of any hormonal contraception. A recent meta-analysis estimated that HC was associated with a 30% reduced likelihood of BV.²⁵ With these assumptions, we will have reasonable power to detect a 30% or greater difference in incidence of BV by CVR status (Table 5). However, BV incidence may be lower, and mechanisms for a favorable shift in vaginal microbiome, if affected by CVR, may be heterogeneous. If so, we will still be able to generate important preliminary data in support of the CVR's favorable effect on the vaginal environment through demonstration of improved microbiome maintenance and immune profile; this would support future study of the CVR in populations with higher incidence of BV and other cervicovaginal STI.

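### HSV-2 shedding is hypothesised as a rate and sampled daily, but section 9.1 analyses only log PCR quantity in a mixed model that ignores clustering of days within a woman

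*Combined protocol and SAP*

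**What the plan says.** - **Hypothesis.** Section 1.1 expects the ring to lead to "decreased rates of HSV2 shedding". Section 1.2 speaks only of a reduction in shedding among HSV-2-infected women, without saying on what scale.
- **Status.** HSV-2 shedding is an exploratory aim in section 2 and a secondary analysis in section 9.1 (Aim 3).
- **Sampling.** Section 5.2.2 and Table 1 (footnote 9) have HSV-2-infected women take an extra daily swab in the month before ring start, the month after start and the month after stopping. Sections 6.3.1, 6.3.3 and 6.3.5 put each period at 30 days.
- **Analysis.** Section 9.1 (Aim 3) measures HSV-2 quantity by PCR and continues: "This will be log transformed and association with CVR use examined using a linear mixed model as for Aim 1". The Aim 1 model it points to "will be log transformed and analyzed using a linear mixed model with subject random effect to account for correlation within person".
- **Nearby text.** The Aim 1 paragraph also says "All available follow-up observations will be used" and "Binary outcomes will be analyzed using generalized estimating equations with log link and robust standard errors". The Aim 2 paragraph allows non-parametric methods or dichotomising with GEE when data are highly skewed. None of these sentences mentions HSV-2, and no section names a binary HSV-2 outcome.

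**The concern.** A shedding rate is the share of days on which virus is detected. The plan collects the data for it but names no analysis of it. The one analysis named takes logs of a quantity that is zero on every negative day, so those days must either be given a value or be left out.

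- **Given a value.** The outcome then carries the shedding rate in part. But one random intercept per woman assumes that, given the woman, today's swab says nothing about tomorrow's. If shedding runs in episodes, the model overstates the information in about 30 consecutive swabs, its standard error is too small, and a ring effect can be declared too often.
- **Left out.** The model compares load on positive days only, and a change in the number of positive days does not enter it.

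Either way, the reported result would not be a sound test of the hypothesis in section 1.1.

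**Working it through.** **Figures from the documents.** Section 9.2 expects about half of 120 women to be HSV-2-infected: 120 × 0.5 = 60, as stated. Applying its 75% return figure to them gives 60 × 0.75 = 45. The level is two-sided 0.05 (section 9.1), with 30 swab-days per period. The documents give no shedding rate, viral load, detection limit, carry-over or power for HSV-2, so there is no stated HSV-2 result to reproduce. All other inputs below are assumptions.

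**Step 1: false positives with negatives kept, closed form.** Let r be the lag-1 carry-over between days within a woman, fading as r^k at lag k. The variance of a 30-day mean, relative to independent days, is

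V = 1 + 2 × Σ(k=1..29) (1 − k/30) × r^k.

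A test that assumes independent days has a true false-positive rate of 2 × [1 − Φ(1.96/√V)].

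| r (assumed) | V | 1.96/√V | False-positive rate |
|---|---|---|---|
| 0 | 1.00 | 1.96 | 5.0% |
| 0.18 | 1.42 | 1.64 | 10.0% |
| 0.3 | 1.82 | 1.45 | 14.6% |
| 0.6 | 3.75 | 1.01 | 31% |

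**Step 2: simulation of the same null case.** Assumptions: 45 or 60 women; 30 days per period; mean shedding 10% or 20% of days, varying between women; two-state Markov carry-over; 4 log10 copies when positive; random-intercept model; 2,000 runs per cell. With 1 copy substituted for negatives, the mixed model was significant in 4.7–5.2% of runs at r = 0, 12.6–14.3% at 0.3 and 31.0–31.2% at 0.6. With 10^2 copies substituted (60 women, r = 0.6) it was 27.1–28.9%. Log-link GEE on shedding days, clustered on woman, stayed at 4.3–6.3%. A separate simulation without a small-sample correction gave 6–7% for that analysis.

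**Step 3: shedding days truly halved, load unchanged (1,000 runs per cell).**
- Negatives kept: expected difference = −0.5 × rate × (4 − s), with s the substituted log10 value. For rates of 10% and 20% this is −0.20 and −0.40 log10 at s = 0, and −0.10 and −0.20 at s = 2. The size depends on s. The mixed model was significant in 93–100% of runs.
- Negatives dropped: estimates from −0.011 to +0.006 log10, significant in 4.3–6.4% of runs, which is chance.
- GEE on shedding days: ratio 0.49–0.51, significant in 73–99% of runs at r = 0.6 and about 100% at r = 0.

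**Step 4: the reverse case.** Load falls by 0.5 log10 and the rate is unchanged (45 women, 28 swabs per period, 10–30% shedding days). The rate analysis is significant in about 6% of runs. Quantity is significant in 14–79% with substitution and 80–100% on positive days only. Each outcome misses something the other sees.

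**The case against.** **HSV-2 carries little weight in this study.** It is exploratory or secondary, no power claim rests on it, and the formal hypothesis in section 1.2 does not say rate. Quantity is a fair measure of reduced shedding. This stands: it limits the importance of the point and is why quantity should be kept.

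**The inflation depends on an input the documents do not give.** With no carry-over there is none. The mention of herpes episodes in section 8 concerns swab irritation and is no evidence on day-to-day correlation. This also stands. But independence of consecutive daily swabs is an assumption too, and 0.18 is enough to double the error.

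**Section 9.1 already has a binary method and a fallback for skewed data.** It does, but neither is tied to HSV-2, and no binary HSV-2 outcome exists for them to act on.

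**Stronger readings that the documents do not support:**
- *The plan will drop negative swabs and so miss a halving of shedding.* The sentence "All available follow-up observations will be used" belongs to the Aim 1 paragraph, but Aim 3 borrows that model, so the text points towards keeping negatives. If they are kept, a halving is found in 93–100% of simulated runs.
- *The rate should replace quantity.* Step 4 shows what would be lost.
- *The Aim 1 primary outcome is undermined because no value is set for undetected* L. crispatus. The plan does leave that value open. But with no true effect, substituting 1, 10^2 or 10^3 copies gave 5–6% false positives each time. What moves is mainly the effect size. Its sign is not guaranteed if loads change as well: with detection rising from 40% to 55% and mean detected load falling from 6 to 5 log10, the difference is 0.55 × (5 − s) − 0.40 × (6 − s), which is +0.35, +0.05 and −0.10 for s = 0, 2 and 3. The value should be fixed before the data are seen, but it is a detail of specification.

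**Conclusion.** The point holds for HSV-2 and is worth acting on. The plan hypothesises a shedding rate, collects daily swabs for it, and names no analysis of it. The one model named, with negatives kept, has a false-positive rate of about 5%, 10%, 15% and 31% at assumed carry-over of 0, 0.18, 0.3 and 0.6. These figures rest on 30 days per period, correlation that fades geometrically, and a subject random effect read as a single intercept. With negatives dropped, which the text disfavours, the model does not respond to shedding frequency at all. No primary outcome is affected. The mismatch between hypothesis and outcome is plain from the text. The size of the error inflation is conditional on carry-over that only the data can show.

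**What to change.** In section 9.1, Aim 3:

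1. Name the proportion of swab-days with HSV-2 DNA detected as the outcome that tests the shedding-rate hypothesis. Compare the swab month before ring start with the month after start, using the log-link GEE with robust errors already in section 9.1, clustered on woman.
2. Keep HSV-2 quantity as a companion outcome, since the rate alone misses a fall in load. Use errors robust to clustering over days within woman, and state how negative swabs enter.
3. Classify swab-days between Months 6 and 7 by actual ring use and report that contrast descriptively. Table 1 (footnote 2) expects about a quarter to stop: 60/4 = 15 HSV-2-infected women, or about 45/4 ≈ 11 after 75% return.

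The cost is a few sentences and one more analysis with standard software; no new data are needed. Nominal power falls under strong carry-over: for a true halving at an assumed 0.6, GEE is significant in 73–99% of runs against 93–100% for the mixed model. Part of that apparent advantage comes from the mixed model's false-positive rate of about 31% there.

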2 STUDY OBJECTIVES

We propose to assess potential benefits associated with both intermittent (use for 3 weeks, remove for 1 week, as defined in the package insert) and continuous (use for 4 weeks, then replace) CVR use

[figure not shown]
among women either with BV or at high risk for BV. We will also recruit women who are HSV2-infected.

Primary outcomes will be as follows:

- The primary outcomes will be the quantity of *L. crispatus* determined by species-specific qPCR assay (Aim 1), local immune parameters, including cytokines and innate mediators (Aim 2), and incidence of and time to clinical BV episodes over the course participation (with the exploratory aim of measuring genital HSV-2 shedding among HSV-2 seropositive women (Aim 3).
- Secondary objectives will include a determination of Nugent score on Gram stain of vaginal fluid, vaginal colonization with bacteria associated with BV, the vaginal microbiome as determined with broad range 16S rRNA and pyrosequencing, and rates of adverse events with CVR use. At study end, all participants will be offered the choice of continuing NuvaRing use, or will be counseled on alternative (non-CVR) contraception methods. Women who opt to switch to an intrauterine device (IUD) at the end of the study will be offered participation in IUD an Extension Study, in which we will follow subjects for an additional 6 months to assess changes in immunity and the microbiome after IUD placement.

[figure not shown]

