5.2.2 Daily Home Swab Samples

For one month before CVR initiation, one month after, and one month following CVR discontinuation, all subjects will be asked to self-collect two vaginal swabs daily and to store in their freezer for return to the clinic at the next visit or beforehand at their convenience. These swabs will be analyzed for vaginal bacteria with bacterium-specific qPCR assays. Women with HSV-2 infection will be asked to collect one additional mixed anogenital swab to measure daily HSV-2 genital shedding. IUD Extension Study participants will be asked to complete two vaginal swabs daily (plus an additional swab for women with HSV-2) at two additional time points: one month after IUD placement, and 6 months after IUD placement. If a subject withdraws from the study due to CVR side effects or other issues and has used the CVR for at least 2 cycles, we will ask that they complete one final month of daily home swab collection.

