6.3.1 Month 1 Visit

A pelvic exam will be performed and study specimens will be collected. Information on symptoms, sexual behavior, antibiotic and hormone use, condoms and douching will be collected via interview and questionnaire. Subjects will be provided with a daily home collection kit and instructions for collecting specimens over the 30 days prior to CVR initiation. Subjects will also receive their HSV and HIV test results at this visit.

For women enrolled in the *optional hormonal sub-study*, additional specimens may be collected (see Section 6.3.2 below), if within the cycle day window and if not already collected at Enrollment.

Vaginal biopsy will be offered at this visit. Women who choose to participate will sign the vaginal biopsy consent form and the biopsies will be collected. For women enrolled in the *optional hormonal sub-study*, the Month 1 vaginal biopsies will ideally be collected at the cycle day 6-10 (follicular phase) visit.

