6.3.2 Hormonal Sub-Study Visit 1b (Cycle day 6-10 or Cycle day 20-25)

For women enrolled in the hormonal sub-study, additional samples will be collected at two specific time points during their menstrual cycle prior to CVR initiation: follicular phase (cycle day 6-10) and luteal phase (cycle day 20-25).

- The first visit will be timed to occur at Enrollment or Month 1, depending on cycle day.
- The second (and additional) visit (Visit 1b) will occur outside their monthly study visits, timed to capture their other cycle phase; either before or after Month 1 depending on cycle timing. Procedures at Visit 1b will be identical to the monthly visits.

Additional Sub-Study Samples: At each sub-study visit, a cervical cytobrush specimen will be collected during the pelvic exam and blood will be drawn (1.0 mL) to measure progesterone levels.

6.3.3 Month 2

A pelvic exam will be performed and study specimens will be collected. Information on symptoms, sexual behavior, antibiotic and hormone use, condoms and douching will be collected via interview and questionnaire. In addition, CVR will be initiated at this visit. Daily home swab samples from the previous 30 days will be collected and reviewed. Subjects will be provided with a new daily home collection kit and instructions for collecting specimens over the next 30 days following CVR use.

6.3.4 Months 3, 4 and 5

A pelvic exam will be performed and study specimens will be collected. Information on symptoms, sexual behavior, antibiotic and hormone use, condoms and douching will be collected via interview and questionnaire at each visit. New CVRs will be dispensed. At the Month 3 visit, daily home swab samples from the previous 30 days will be collected and reviewed.

For women enrolled in the *optional hormonal sub-study*, at the Month 3 visit, a cervical cytobrush specimen will be collected during the pelvic exam and blood will be drawn (1.0 mL) to measure progesterone levels.

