6.3.5 Month 6 - Stop CVR

A pelvic exam will be performed and study specimens will be collected. Information on symptoms, sexual behavior, antibiotic and hormone use, condoms and douching will be collected via interview and questionnaire. Participants will be asked if they wish to discontinue CVR at this visit. Those who elect to

stop will be provided with non-hormonal contraception (condoms). Subjects who wish to continue using CVR will be provided a new ring at this visit. All subjects will be asked to collect daily swabs at home over the next 30 days. Home collection kits and instructions will be provided. Vaginal biopsies will be collected at this visit, for women who choose to participate and had baseline biopsies at the Month 1 visit.

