26. Paul A. Harris, Robert Taylor, Robert Thielke, Jonathon Payne, Nathaniel Gonzalez, Jose G. Conde, Research electronic data capture (REDCap) - A metadata-driven methodology and workflow process for providing translational research informatics support, *J Biomed Inform*. 2009 Apr;42(2):377-81.

Table 1. Laboratory specimens to be obtained at each visit or by self-collection

Test	Screen	Enroll	Month 1 Baseline	Month 1b substudy ¹	Month 2 CVR Start	Month 3-5	Month 6 ²	Month 7	Month 8 ¹²	Month 9 (IUD 1)	Month 9 (IUD 2)	Month 10-12 (IUD 3-5)	Month 13 (IUD 6)	Month 14 (IUD 7)
Microbiome														
pH measurement	X	X	X		X	X		X	X	X	X		X	X
Saline microscopy	X	X	X		X	X		X	X	X	X		X	X
Gram stain	X	X	X	DSC	X	X	DSC	X	X	DSC	X		X	DSC
Bacterial qPCR assays ³		X	X	DSC	X	X	DSC	X	X	DSC	X		X	DSC
Broad-range 16S rRNA PCR pyrosequencing		X	X	DSC	X	X	DSC	X	X	DSC	X		X	DSC
Cervical cytobrush ⁴			X		X		X ⁵				X			X
Vaginal biopsy ¹³			X				X						X	
Immune environment														
CVF: mucosal immune mediators ⁶ , proteomics			X	X	X	X	X	X	X	X	X		X	X
Progesterone level ⁷				X	X		X ⁵				X			X
STI acquisition/shedding														
NAAT: C. trachomatis , N. gonorrhoeae , T. vaginalis			X	X ⁸	X ⁸	X ⁸	X ⁸	X ⁸	X ⁸					
HSV PCR vaginal swab ⁹				DSC		DSC		DSC		DSC				DSC
HSV serology			X						X ¹⁰					
HIV serology			X						X ¹⁰					
Urine Pregnancy Test	X	X ¹¹	X ¹¹	X ¹¹	X ¹¹	X ¹¹	X ¹¹	X ¹¹	X ¹¹					
Clinical exam for LGTI		X	X					X		X				X
IUD supplement														
Monthly phone calls for retention												X		

Abbreviations: DSC = daily self-collection, BVAB = bacterial vaginosis-associated bacteria, CVF = cervicovaginal fluid, NAAT = nucleic acid amplified test, HSV = herpes simplex virus, LGTI = lower genital tract infection (BV, VVC, cervicitis, genital ulcer disease), PCR = polymerase chain reaction.

¹ Only women enrolling in the optional Hormonal sub-study will be asked to come to the clinic for visit 1b procedures.

² We anticipate that approximately ¼ of subjects will elect to discontinue CVR use at the end of the study; all participants will be invited to perform daily self-collection of vaginal swabs as noted during the month after CVR cessation.

³ Vaginal bacterial assays include qPCR for *G. vaginalis*, *Megasphaera* phylotypes 1 and 2, *L. crispatus*, *L. jensenii*, and *L. iners*.

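### Aim 3's HSV-2 model names only a subject random effect for daily swabs; if days are rows, short-range serial correlation makes the CVR standard error too small

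*Combined protocol and SAP*

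**What the plan says.** Section 9.1, Aim 3, makes the quantity of HSV-2 by PCR a secondary analysis and gives its method in one sentence: "This will be log transformed and association with CVR use examined using a linear mixed model as for Aim 1". The Aim 1 model is a "linear mixed model with subject random effect to account for correlation within person". Robust standard errors appear in the same paragraph, but only for binary outcomes analysed by GEE. For the mixed model, no residual structure, random CVR effect or robust standard error is named. The end of the Aim 2 paragraph sets a two-sided 0.05 level for all analyses.

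The data come from home collection. Section 5.2.2 asks women with HSV-2 for "one additional mixed anogenital swab to measure daily HSV-2 genital shedding", and Table 1 lists HSV PCR only as daily self-collection. The blocks are set by the visit schedule:
- Section 6.3.1 (Month 1): "collecting specimens over the 30 days prior to CVR initiation".
- Section 6.3.3 (Month 2, ring start): "collecting specimens over the next 30 days following CVR use".
- Section 6.3.5 (Month 6): "All subjects will be asked to collect daily swabs at home over the next 30 days".

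Table 1, footnote 2, expects about a quarter "of subjects will elect to discontinue CVR use at the end of the study". Section 9.2 anticipates 60 HSV-2-infected women. Section 2 describes this part of Aim 3 as exploratory ("with the exploratory aim of measuring genital HSV-2 shedding among HSV-2 seropositive women").

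**The concern.** Aim 1 describes its model for *L. crispatus* at follow-up visits, which are monthly. Aim 3 carries it over to swabs taken on consecutive days. A subject intercept allows for a woman being a high or low shedder overall. It does not allow for today resembling yesterday more than it resembles a day three weeks ago. The CVR contrast compares long runs of adjacent days, and in that layout unmodelled short-range correlation matters most, because 30 swabs in a block carry less information than 30 independent ones.

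At stake is the error rate for a named hypothesis: section 1.2 expects reduced HSV-2 shedding with CVR use. If the standard error is too small, the analysis will report an effect that does not exist more often than 5% of the time, and its confidence intervals will be too narrow.

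**Working it through.** **Plan's own figure.** The documents give no standard error, power or correlation for HSV-2 quantity. The one figure that can be reproduced is the number of women: 120 × 0.5 = 60.

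**Inputs from the documents.** 60 women (9.2); 30-day blocks (6.3.1, 6.3.3, 6.3.5); two-sided 0.05 (9.1).

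**Assumed.** Each day is a row; random intercept; independent residuals in the fitted model; every day has a value; no missing swabs; ring status constant within a block; residual SD 1 (the SE ratio does not depend on it). True residuals follow AR(1) with correlation ρ.

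**Formulas.** With two adjacent blocks of n = 30 days and N = 60 women, the random-intercept estimate is the difference of block means.
- Variance of one block mean: (1/n)(1+ρ)/(1−ρ) − 2ρ(1−ρⁿ)/[n²(1−ρ)²].
- Covariance of adjacent block means: ρ(1−ρⁿ)²/[n²(1−ρ)²].
- True SE = √{2(variance − covariance)/N}.
- Model SE = √{s² × (2/30)/N}, where s² is the residual variance that the model estimates.
- Type I error = 2Φ(−1.96 × model SE/true SE).

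**Worked case, ρ = 0.5.**
- Block-mean variance = 3/30 − 1/(900 × 0.25) = 0.1000 − 0.0044 = 0.0956.
- Covariance = 0.5/(900 × 0.25) = 0.0022.
- True SE = √{2 × (0.0956 − 0.0022)/60} = 0.0558.
- Variance of a woman's 60-day mean = 3/60 − 1/(3,600 × 0.25) = 0.0489. Her within-woman sum of squares is 60 − 60 × 0.0489 = 57.07, or 3,424 over 60 women. The fitted CVR effect removes about 60 × 15 × 0.0031 = 2.8. So s² = 3,421/(60 × 59 − 1) = 0.967.
- Model SE = √{0.967 × (2/30)/60} = 0.0328.
- Ratio = 0.588; error = 2Φ(−1.152) = 24.9%.

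| AR(1) ρ | Model SE | True SE | Ratio | Type I error |
|---|---|---|---|---|
| 0 | 0.0333 | 0.0333 | 1.00 | 5.0% |
| 0.1 | 0.0333 | 0.0367 | 0.907 | 7.5% |
| 0.2 | 0.0332 | 0.0404 | 0.822 | 10.7% |
| 0.3 | 0.0331 | 0.0447 | 0.741 | 14.7% |
| 0.5 | 0.0328 | 0.0558 | 0.588 | 24.9% |

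Simulation agrees: 10–11% at ρ = 0.2 and 25% at ρ = 0.5.

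**Variations, by simulation.**
- Third block added, a quarter of women off the ring: 5, 7, 11, 15 and 24%.
- 45 women (0.75 × 60, borrowing the return rate in 9.2): 5, 7, 11, 15 and 26%.
- REML fit, three blocks, 20% of swabs missing: 12% at ρ = 0.2 and 24% at 0.5.

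**Patterns that do not inflate the error.**
- Constant correlation of 0.5 or 0.8 between every pair of days: ratio 1.00, error 5.0%. The shared part cancels in the difference.
- A 28-day cyclic residual with lag-1 correlation 0.49: ratio 1.41, error 0.6%. The cycle counts as residual variance but nearly averages out over 30 days, so the standard error is too large.

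**Remedies under AR(1).** Woman-clustered errors with a t reference on N − 1, and paired means per woman per period, gave 4–6% throughout.

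**The case against.** **The plan does not commit to the faulty model.** It does not say that rows are days, that the random effect is an intercept, or that residuals are independent. A model with serial residuals, or with one summary per period, would fit the same wording. This stands, and it makes the point conditional. It does not remove it: no summary is mentioned, section 9.1 says under Aim 1 that all available observations will be used, and the swab's stated purpose is daily measurement. A clinic-visit reading is not available, since Table 1 shows HSV PCR only as daily self-collection.

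**A reader might infer that any positive day-to-day correlation inflates the error.** That is false. The constant and cyclic cases above show that the direction depends on the pattern, not only on the sign. Only correlation that decays with lag, beyond the intercept, supports the point.

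**The size rests on assumed inputs.** This also stands. The documents give no correlation, shedding frequency or episode length. Correlation of 0.8 would give 49%, and a reader might take an error near one in two from that, but nothing in the documents supports so high a value.

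**Negative swabs.** Quantity is to be logged, and the plan does not say what value a negative swab takes. The table gives every day a value. If only positive swabs were modelled, the inflation would be smaller. With 10% of days positive and shedding in runs averaging 1.25, 2 or 3 days (all assumed), simulation gave about 6–8, 9–14 or 13–23%. Giving every day a value under the same run lengths gave 7, 19 or 32%.

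**Low stakes.** No sample size or primary conclusion depends on this outcome. That is right, and it sets the priority.

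**Conclusion.** The point holds in conditional form. If the Aim 1 model is fitted to daily HSV-2 rows with a random intercept and independent residuals, positive serial correlation that fades with lag makes the CVR standard error too small. Over the assumed AR(1) range of 0 to 0.5, the type I error runs from the nominal 5% to about 25%. The low end means no problem, and the documents cannot say where in the range the truth lies. The figures also rest on 60 women, complete 30-day blocks with constant ring status and a value for every swab. Women on the 21-day schedule have ring-free days in the block after ring start, so ring status is only largely constant there.

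The documents do not support extending the point to the primary outcomes of Aim 3, which are incidence of and time to BV. The outcome affected is secondary in section 9.1 and exploratory in section 2, so this is a low-priority correction.

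**What to change.** In section 9.1, Aim 3, specify one of the following for HSV-2 quantity:
- the mixed model with standard errors clustered on the woman and a small-sample reference, for example t on the number of women minus 1; or
- a paired comparison of one mean log quantity per woman per CVR period.

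Neither depends on the day-to-day correlation pattern. A serial residual structure inside the mixed model is another route, but it protects the error rate only if the chosen structure fits. The same sentence should say what value a negative swab takes, because the period mean depends on it.

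**Cost.** One sentence and no new data. Intervals widen by the inverse of the SE ratio: 1/0.907 = 1.10, 1/0.822 = 1.22, 1/0.741 = 1.35 and 1/0.588 = 1.70 times at correlations 0.1, 0.2, 0.3 and 0.5. They are essentially unchanged if days are independent. The paired version loses women with no swabs in one of the periods. The small-sample reference matters if few HSV-2-positive women enrol: clustered errors with a normal reference gave 8–9% error with 10 women and about 6% with 20, against 4–5% with the t reference.
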